- Eligibility Source documents: Initial consult note, pre-implant sleep study, pre-implant DISE report, HGNS titration report, HGNS efficacy sleep study report (if applicable), current medications list (reconciled), all Inspire® therapy reports leading up to enrollment.

4C. Study Timeline - Pages 5 to 10

- Enrollment (Study Day 1): HGNS therapy will be deactivated (set to 0.0 V) for one week. Sham threshold determination may be done during this visit, or during randomization visit (see below study week 2). RSC will schedule cardiovascular and sympathetic testing, if possible. The patient will also be instructed about neurobehavioral testing and will perform a practice administration of the DSST and PVT. Form 1 will be completed by RSC (remote #, current therapy status, non-dominant arm diameter, WatchPAT digit determination, medication reconciliation, sham threshold determination (volts), and active therapy setting (volts)). If needed, the patient will contact RSC after the appointment to provide the remote number. The patient will also be given an "on-study card" containing contact information for the research coordinator. The patient will be told to contact the coordinator if any health care providers intend to make changes to the patient's blood pressure medication. An enrollment questionnaire will be completed by the patient:
 - o Do you take any medications or substances to improve daytime alertness?
 - Do you take any medications or substances to improve sleep quality?
 - o How many hours do you sleep each night, on average?
 - ESS, ISI, FOSQ, Snoring VAS
- Washout Period 1 (Study Week 1): The patient will not use HGNS for 1 week
- Randomization Visit (Study Week 2 with [name] and RSC):
 - a. Patient will fill out "washout questionnaire":
 - Patient attestation statement about therapy non-use
 - Have you taken any substance to increase daytime alertness (e.g. caffeine)?
 - Have you taken any substance to improve sleep quality (e.g. alcohol)?
 - o Have you had any episodes of falling asleep while driving?

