- b. Sham Threshold Determination (Consent or Randomization Visit): Mouth open, nose breathe only, stimulation from 0.1V up by 0.1-0.2V at same electrode configuration as at last clinic visit, level at which bulk tongue motion detected without obvious protrusion. This process is repeated and the average value is used to determine "sham-HGNS". This threshold will be used to define "sub-therapeutic amplitude" (sham). The electrode configuration will remain consistent between the patient's therapeutic and sham thresholds.
- c. Randomization: The research coordinator will program the device at the specified amplitude level: either "sham-HGNS" as above, or "therapeutic HGNS," depending on which is assigned first (**see part d below**). The "therapeutic HGNS" setting will be the patient's incoming amplitude on enrollment day which will have been predetermined as part of routine clinical care prior to enrollment in the study. The patient control range will be deactivated for consistency, i.e. there will only be one allowable setting. The research coordinator will instruct the patient to use therapy the same night, and for every night until the next washout after cardiovascular test day (study week 6).
- d. Randomization technique: Both patients and investigators will remain blinded regarding patient intervention (sham or treatment HGNS). Only the research coordinator will remain unblinded; he will randomize the patients using a simple scheme (sealedenvelope.com) and will not take part in any assessments. Block design (block size = 10 with 10 units per block) for total of 100 potential subjects. Number 1 = Sham First, Number 2 = Treatment First.
- Blinding Adequacy Phone Call (Week 2, Day 2)

A blinded member of the study team, as delegated by the PI, will contact the patient and perform a verbal questionnaire:

- 1. Do you think you are on "low" or "regular" treatment, or do you not know?
- 2. Why you do think so?
 - a. Increased snoring per bed partner
 - b. Increased fatigue
 - c. Morning headache
 - d. Nighttime awakening
 - e. Other
- Weekly Check-In Phone Call (Week 3, Week 4, Week 5)

RSC weekly call with patient re: usage. Goal is to encourage use (>20h/week) RSC will document changes in blood pressure medication, if applicable. RSC will remind the patient to consistently take the blood pressure medication. Any questions, comments, concerns, or AEs will be documented at this time as well.

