- Sympathetic Measurements (Study Week 6, Day 2): The patient will be laid supine in a comfortable position prior to testing. The 15-minute protocol will involve pre-ejection period (PEP) testing by impedance cardiography.

Prior to the testing, subjects will have been informed of the pre-visit protocol: no food >6 hours before testing; withhold all cardiac and blood pressure medications on the day of testing; no caffeine or alcohol >12 hours before testing; avoid exercise on morning of testing; refrain from cigarette smoke exposure >12 hours before testing; and abstain from vitamin supplementation >72 hours before testing.

Pre-ejection Period (PEP): Each patient will be fitted with the Biopac NICO100C Impedance Cardiography (ICG) Noninvasive Cardiac Output Module (Biopac, Goleta CA USA). This device will record the ECG and the ICG continuously during a 10-minute period through eight, disposable, pre-gelled Ag/AgCl electrodes. PEP will be calculated as the average interval (milliseconds) from the onset of left ventricular depolarization, reflected by the Q-wave onset in the ECG to the opening of the aortic valve, reflected by the B-point in the ICG signal.

- o At the end of this visit, the patient will be set to 0.0V for washout period 2.
- Procedure Day Questionnaire: Therapy attestation statement, medication reconciliation, caffeinated beverages per day, sleep-promoting substance use (e.g. alcohol), ESS, FOSQ, ISI, Snoring VAS.
- Neurobehavioral Measurements (Study Week 6, Day 2): The patient will perform neurobehavioral tests on a designated laptop in a quiet room at the Otorhinolaryngology clinic. Each subject will perform a unique version of the digital symbol substitution test

and psychomotor vigilance test. The laptop is calibrated for timing precision. All patients will be monitored by a trained study staff member to ensure adherence to test procedure protocol.

Prior to testing, subjects will have been informed of pre-visit protocol: abstain from testing if sick; abstain from testing if <1 hour of waking up; and abstain from testing if >16 hours of being awake.

- Washout Period 2 (Study Week 6-7): The patient will not use HGNS for 7 days.

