- Crossover Visit & Therapy (Study Week 7): The patient will be switched to the other intervention arm (treatment to sham vs. sham to treatment) for 28 days, or for the duration spent on the previous intervention arm. The research coordinator will program the device at the specified amplitude level, per Form 1.

Patient will fill out "washout questionnaire #2":

- Patient attestation statement about therapy non-use.
- Have you taken any substance to increase daytime alertness (e.g. caffeine)?
- Have you taken any substance to improve sleep quality (e.g. alcohol)?
- o Have you had any episodes of falling asleep while driving?

The research coordinator will reprogram the patient's HGNS to the amplitude the patient was using prior to study participation. The research coordinator will instruct the patient to use therapy the same night.

• Blinding Adequacy Phone Call (Week 7, Day 2)

Phone call: second morning questionnaire:

- 1. Do you think you are on "low" or "regular" treatment?
- 2. Why you do think so?
 - a. Increased snoring per bed partner
 - b. Increased fatigue
 - c. Morning headache
 - d. Nighttime awakening

e.	Other					

Weekly Check-In Phone Call (Week 8, Week 9, Week 10)

RSC weekly call with patient re: usage. Goal is to encourage use (>20h/week). Document any changes in blood pressure medication.

Document any AEs, issues or concerns.

• 24-hour Ambulatory Blood Pressure & WatchPAT (Study Week 9, Night 1):

The patient will be programmed and mailed 24-hour ambulatory blood pressure testing (ABP) and WatchPAT, scheduled to arrive between 2-7 days before physiology testing.

RSC will ensure that ABP, WatchPAT and Inspire® times are synchronized. For convenience and/or patient preference, the patient may meet with RSC in person to pick up the equipment.

- Sympathetic, Vascular, & Neurobehavioral Measurements & Wrap-Up (Study Week 10, Day 2):
 - 1. RSC will download therapy compliance data from the patient's remote.
 - 2. The patient will undergo the same set of testing as above.
 - 3. If any of the ABP or WatchPAT data is invalid or incomplete, the patient may be asked to repeat these tests, at the discretion of the PI. In this case, the patient will remain at the current setting and will need to return to have their HGNS reset to the pre-study amplitude.
 - 4. Procedure Day Questionnaire: Therapy attestation statement, medication reconciliation, caffeinated beverages per day, sleep-promoting substance use, ESS, FOSQ, ISI, Snoring VAS.

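### Treatment-first patients have no listed contact during or after sham that asks directly about dozing at the wheel; for sham-first patients the question comes late

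*Combined protocol and SAP*

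**What the plan says.** Section 4C lists the direct question, "Have you had any episodes of falling asleep while driving", in the washout questionnaire at the week 2 visit and again in washout questionnaire #2 at the week 7 crossover visit. Each follows about a week at 0.0 V and comes before the first night on the next setting. Neither states a recall period.

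At week 7 "The patient will be switched to the other intervention arm (treatment to sham vs. sham to treatment) for 28 days", or for as long as the first period lasted. Treatment-first patients therefore begin sham that day.

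Contacts within each period list other content:

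- The blinding calls, for example "Blinding Adequacy Phone Call (Week 7, Day 2", ask for a guess at the setting and the reasons for it.
- The weekly calls by the coordinator cover usage and blood pressure medication, and in weeks 3 to 5 "Any questions, comments, concerns, or AEs will be documented at this time as well". The calls in weeks 8 to 10 have an equivalent line.
- The Procedure Day Questionnaire at week 6 consists of "Therapy attestation statement, medication reconciliation, caffeinated beverages per day, sleep-promoting substance use (e.g. alcohol), ESS, FOSQ, ISI, Snoring VAS". The week 10 list is essentially the same.
- An Exit Questionnaire is named at week 10 without its items.

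Section 7 expects OSA symptoms to return in the sham period and advises caution with driving then. Section 2 excludes patients with a sleep-related driving accident or near miss in the year before implantation.

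**The concern.** The protocol treats sleepiness at the wheel as a risk worth a direct question after one week without therapy. In the treatment-first sequence it lists no such question after up to four weeks of sham, the period its own risk section warns about. A patient who nods off briefly without consequence may not think of it as an adverse event to volunteer. An episode that comes to light only later, or not at all, gives the investigator no chance to restore therapy. What is at stake is patient safety during a deliberate withdrawal of effective treatment. The efficacy comparison is not at issue.

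**Working it through.** The plan gives no figure on this point, so there is none to reproduce. The check places every listed contact in section 4C on the timeline for each sequence.

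| Contact | Driving question listed? | Treatment-first | Sham-first |
|---|---|---|---|
| Week 2 visit | Yes | at 0.0 V, before treatment | at 0.0 V, before sham |
| Week 2 blinding call | No | on treatment | on sham |
| Calls, weeks 3, 4, 5 | No (open AE recording) | on treatment | on sham |
| Week 6 test visit | No | end of treatment | end of sham |
| Week 7 crossover visit | Yes | at 0.0 V, before sham | at 0.0 V, about 7 days after sham |
| Week 7 blinding call | No | on sham | on treatment |
| Calls, weeks 8, 9, 10 | No (open AE recording) | on sham | on treatment |
| Week 10 visit | Not listed; Exit Questionnaire items not given | end of sham | end of treatment |

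**Treatment-first.** On-sham contacts: 1 blinding call + 3 weekly calls + 1 visit = 5. The question is listed at 0 of 5, and at no later contact. If ABP or WatchPAT has to be repeated, the patient stays on the current setting beyond the week 10 visit, still with no listed question. The Figure 3 note in section 4A allows each step to move by 14 days, so sham could last 28 - 14 = 14 to 28 + 14 = 42 days. The order of contacts does not change.

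**Sham-first.** The on-sham count is the same, 0 of 5, but the week 7 question follows. Delay from the start of sham: 28 + 7 = 35 days. If the sham step alone moves by 14 days, the range is 14 + 7 = 21 to 42 + 7 = 49 days. With no recall limit stated, the answer can cover the sham weeks.

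**With the question added to the weekly calls and the test visits.** 3 calls + 1 visit = 4 of 5 on-sham contacts in either sequence. It is first asked about 7 days after sham starts, at the week 3 or week 8 call.

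**Patients concerned.** The allocation ratio is not stated. Assuming equal allocation, 60/2 = 30 treatment-first patients at the planned n = 60. The randomization list is "for total of 100 potential subjects", so at most 100/2 = 50.

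**The case against.** The strongest reply is that general safety capture already covers this. Three weekly calls in each period record adverse events. The definition in section 11 is broad, all events are recorded, and the PI assesses how each relates to the study procedures. ESS and FOSQ are completed at week 10. The highest-risk drivers are excluded and the rest are advised to take care. The question belongs to a washout form, and the protocol never presents it as its monitor for sham.

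Much of this stands. A reader might infer that none of the 28 sham days is covered in treatment-first patients, or that driving episodes would go undetected. The documents do not support that: open-ended recording runs weekly, and the Exit Questionnaire, whose items are not given, might contain the question. What is missing is a listed direct question. Forms completed at the end of the period would also come too late to act on during sham and could miss patients who leave early. Section 10 allows for 10-15% dropout as symptoms return.

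A reader might also count sham-first patients as uncovered. They are not; for them the question is only late.

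The crossover text also says the coordinator will reprogram the device to the amplitude used before the study, which might suggest that nobody starts sham at week 7. The same section requires the switch from treatment to sham, and the design depends on it.

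A last objection concerns blinding: a remedy that paused patients only before sham would reveal allocation. That is right, and it shapes the fix.

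**Conclusion.** The point holds as a gap in direct questioning. In the treatment-first sequence the question is listed at 0 of 5 on-sham contacts and not afterwards, subject to the unknown content of the Exit Questionnaire and with partial cover from open adverse event recording. In the sham-first sequence the next listing is about 35 days after sham starts (21 to 49 if the sham step moves by 14 days).

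These figures count contacts and days. They do not measure risk: no rate of driving episodes is given, so no reduction in harm can be claimed. The figure of about 30 treatment-first patients assumes equal allocation. The number still to be enrolled cannot be derived, since section 9 planned to finish recruitment in 2020 and this version is dated 09/30/2021.

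Severity is minor, and the change is a cheap improvement. The primary analysis and the sample size are unaffected.

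**What to change.** Add the question to the existing weekly calls (weeks 3-5 and 8-10) and to both Procedure Day Questionnaires (weeks 6 and 10), with a recall period running from the last time it was asked. Ask it also at early withdrawal, and at the device reset when repeat testing has delayed it. Use identical wording in both periods.

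Record any positive answer as an adverse event. A blinded investigator should review it promptly and decide whether the patient continues or returns to the pre-study amplitude. The same rule and the same timing must apply whichever setting is current or next.

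Do not add a rule that delays only sham or washout steps. At weeks 2 and 7 every patient is at 0.0 V, so a wait that occurred only when sham came next would disclose allocation to the patient. It could also disclose it to the second person at the "Randomization Visit (Study Week 2 with [name] and RSC"), although under the plan "Only the research coordinator will remain unblinded".

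The cost is one question at contacts that already take place, one at withdrawal or delayed reset, an investigator available for review, and a short note for each positive answer. The downside is slightly longer contacts and a small chance of prompting guesses about allocation, which identical wording and handling in both periods should limit.

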Full Study Title

Hypoglossal Nerve Stimulation for Obstructive Sleep Apnea on Sympathetic and Vascular Function

Short Study Title CARDIOSA-12

Principal Investigator
[name], MSCR
Department of Otorhinolaryngology

Co-Investigator
[name]
Department of Otorhinolaryngology

Sponsors

American Heart Association
American Sleep Medicine Foundation

Protocol Version Number & Date Version 3.4 | 09/30/2021

- 1. Eligibility Criteria: All patients recruited into the study will have already been implanted with the Inspire® device. Additional inclusion criteria include:
 - As tolerating the therapeutic level during sleep can take time (weeks to months), all
 patients must be able to use the device at the therapeutic setting (> 20 hours per week for
 > 1 month) prior to enrollment based on compliance data.
 - The patients will be English-speaking and able to give written informed consent.

2. Exclusion Criteria

- Inspire® remote model 2500 or later is required. Patients with older remotes are not candidates due to limited adherence monitoring capabilities.
- Patients who have fallen asleep while driving resulting in accident or "near miss" accident within 1 year prior to HGNS implantation.
- Pregnant women will be excluded*
- Actively using positive airway pressure (PAP) therapy for treatment of OSA.
- Patients in whom the difference between sham and therapeutic voltages is within 0.1 V of 30% therapeutic voltage.
- * Women of child bearing potential must NOT be pregnant or plan on becoming pregnant. This study involves temporarily stopping treatment of obstructive sleep apnea, which may harm the fetus. If applicable, the patient will need to take a urine pregnancy test after enrollment (prior to washout #1), and again prior to washout #2.

3. Study Objectives

Primary Outcome Measure:

Change in mean 24-HOUR systolic ambulatory blood pressure values

Aim 1: Determine the impact of hypoglossal nerve stimulation on 24-hour systolic ambulatory blood pressure in this cohort of patients with moderate-severe obstructive sleep apnea

Hypothesis: The mean 24-hour systolic blood pressures will be improved at therapeutic levels of hypoglossal nerve stimulation and returned to pre-operative levels after 30-day sham period

Secondary Outcome Measures:

Change in mean 24-HOUR diastolic ambulatory blood pressure values

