Hypothesis: The pulse wave velocity parameters will be improved at therapeutic levels of hypoglossal nerve stimulation and returned to pre-operative levels after 30-day sham period

Change in Digit Symbol Substitution Test (DSST) score

Aim 5: Determine the impact of hypoglossal nerve stimulation on digital symbol substitution test score in this cohort of patients with moderate-severe obstructive sleep apnea

Hypothesis: The digital symbol substitution test score will be improved at therapeutic levels of hypoglossal nerve stimulation compared to after 30-day sham period

Change in Psychomotor Vigilance Test (PVT) score

[figure not shown]
Aim 6: Determine the impact of hypoglossal nerve stimulation on psychomotor vigilance test score in this cohort of patients with moderate-severe obstructive sleep apnea

Hypothesis: The psychomotor vigilance test score will be improved at therapeutic levels of hypoglossal nerve stimulation compared to after 30-day sham period

4. Procedures and Data Collection

4A. *Pre-Study Procedures:* All patients in the cohort will have undergone implantation of HGNS for OSA at the University of Pennsylvania or Thomas Jefferson University as part of their ongoing care for their OSA. HGNS therapy is not experimental and is not under investigation per se for efficacy in this study. **Figure 3** shows the study flow. Patients will receive compensation for travel and time spent in the study (\$100 per visit, plus \$10 parking reimbursement for each cardiovascular measurement visit; total=up to \$520). Reimbursement for parking may also be available. Compensation will be pro-rated, and will be in the form of mailed checks and/or ClinCards.

Figure 3: Study Flow

Note: We will leave +/- 14 days at each step to accommodate for scheduling issues, etc.

- 1. HGNS Device Implantation: Under general anesthesia, the HGNS device is implanted via 3 incisions: right neck (stimulation lead), right upper chest (pulse generator) and right lower chest (respiratory sensor). The incisions are connected via a tunneling device, integrating the system components. The pulse generator, using technology from cardiac pacemakers, utilizes the signal from the pressure sensor for timing of stimulation to the tongue nerve. Patients are monitored in post-anesthesia recovery until stable for discharge. The device remains "off" for 1 month to allow for adequate healing.

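### Section 4C contradicts itself for period 2: its testing labels fall two to three weeks after crossover against a 28-day rule, and one sentence undoes the switch to sham

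*Combined protocol and SAP*

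**What the plan says.** All the period 2 instructions are in Section 4C.

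- **Start.** At the end of the period 1 laboratory visit (Week 6 Day 2), "At the end of this visit, the patient will be set to 0.0V for washout period 2", which lasts 7 days. The crossover visit is in Week 7.
- **Duration.** The new setting is kept "for 28 days, or for the duration spent on the previous intervention arm".
- **Tests.** The labels read "24-hour Ambulatory Blood Pressure & WatchPAT (Study Week 9, Night 1" and "Sympathetic, Vascular, & Neurobehavioral Measurements & Wrap-Up (Study Week 10, Day 2". The monitor and sleep test are mailed, "scheduled to arrive between 2-7 days before physiology testing", or collected in person.
- **Calls.** Weekly check-ins are in Weeks 8, 9 and 10. In period 1 they are in Weeks 3, 4 and 5, before testing in Week 6.
- **Programming.** The crossover entry switches the patient to the other arm, in either direction, using the amplitude on Form 1. After the washout questionnaire, the same entry tells the coordinator to return the device to the amplitude used before the study and the patient to start that night. It does not limit this to one sequence.

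Three other places bear on the reading. The randomization paragraph of Section 4C defines the therapeutic setting as the amplitude the patient arrives with at enrollment. Wrap-up item 6 restores that amplitude at study exit. The Aim 1 hypothesis in Section 3 has pressures "returned to pre-operative levels after 30-day sham period", and Section 7 describes a four-week sham period.

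**The concern.** These sentences tell the coordinator what to program and when to take the primary measurement, and they cannot all be followed.

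Aim 1 is analysed in Section 6 by a paired t-test of sham against active 24-hour systolic pressure. That test needs one value per patient under each setting. It has no term for time spent on the setting, so it relies on the schedule to make the two exposures comparable.

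If the Week 9 label were followed, period 2 would be measured after about half of period 1's exposure. If the restore sentence were followed, a treatment-first patient would be on active therapy in both periods and would have no sham value to pair.

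**Working it through.** **Timing.** Study day = 7 × (week − 1) + day. Section 4C gives only the week of each programming visit, so programming is allowed on Day 0, 1 or 2 of that week. Blood pressure testing is taken on Day 0 or Day 1. Period 1 labels it Day 0-1. The period 2 label says Night 1, which in period 1 is the sleep-test night that follows the blood pressure recording.

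| | Programming | ABP | Days to ABP | Lab visit | Days to lab |
|---|---|---|---|---|---|
| Period 1 labels | Week 2: 7, 8 or 9 | Week 6 Day 0-1: 35-36 | 35 − 9 = 26 to 36 − 7 = 29 | Week 6 Day 2: 37 | 28 to 30 |
| Period 2 labels | Week 7: 42, 43 or 44 | Week 9 Day 0-1: 56-57 | 56 − 44 = 12 to 57 − 42 = 15 | Week 10 Day 2: 65 | 21 to 23 |
| Period 2, if Week 11 | Week 7: 42, 43 or 44 | Week 11 Day 0-1: 70-71 | 70 − 44 = 26 to 71 − 42 = 29 | Week 11 Day 2: 72 | 28 to 30 |

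The plan's own figure of 28 days is reproduced by the period 1 labels, which supports the day count. It is not reproduced by the period 2 labels. The alternative in the duration rule, matching the previous arm, does not help, because period 1 is also about 28 days.

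The gap does not depend on the day convention. With the same weekday conventions in both periods, Week 2 to Week 6 is 4 weeks and Week 7 to Week 9 is 2 weeks, a shortfall of 14 days for the primary measurement. Week 7 to Week 10 is 3 weeks, a shortfall of 7 days for the laboratory tests.

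Three internal checks on the Week 9 label:

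1. *Kit arrival.* Two to seven days before a Week 10 Day 2 lab visit is day 65 − 7 = 58 to 65 − 2 = 63. The labelled test on day 56-57 comes before a mailed kit would arrive. Only in-person collection makes it possible.
2. *Test sequence.* Wrap-up repeats the period 1 tests. Counting back from the Week 10 lab visit in the period 1 order puts ABP at Week 10 Day 0-1 (days 63-64), which is 63 − 44 = 19 to 64 − 42 = 22 days after programming. That agrees with neither the Week 9 label nor the 28-day rule.
3. *Calls.* In period 1 the calls are 1, 2 and 3 weeks after programming and testing is in week 4. The same pattern from Week 7 gives calls in Weeks 8, 9 and 10, as printed, and testing in Week 11.

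A 28-day period from day 42, 43 or 44 ends on day 70, 71 or 72, which is also Week 11.

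**Programming.** The crossover instructions by sequence:

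| Sequence | Due in period 2 | Switch using Form 1 | Restore pre-study amplitude | Compatible? |
|---|---|---|---|---|
| Sham first | Therapeutic | Therapeutic | Therapeutic | Yes |
| Treatment first | Sham | Sham | Therapeutic | No |

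The restore sentence comes second and is followed by the instruction to begin that night, so it reads as the last programming step of the visit.

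**The case against.** The strongest reply is that the documents show what is meant. The 28-day rule is explicit, and Sections 3 and 7 agree with it. The call weeks point to Week 11. The crossover entry names both directions of the switch, and Form 1 holds both voltages. Wrap-up items 3 and 6 provide for a return to the pre-study amplitude at exit, which makes most sense if some period 2 patients are on another setting. The coordinator who programs the device is unblinded and can see which arm is due. On this view the labels are slips of numbering and the sentence is misplaced.

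Most of that stands. It settles the probable intent and keeps the severity moderate. It does not remove the contradiction from text that staff are meant to follow, and because only the coordinator is unblinded, blinded colleagues are poorly placed to notice a programming error.

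The scheduling note in Section 4A, "We will leave +/- 14 days at each step to accommodate for scheduling issues", may absorb the timing gap in practice. It is a tolerance around the nominal schedule and does not say which nominal date is right. It has no bearing on the programming conflict.

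The programming day within the week is not stated, so a single exact day count would be false precision; only ranges are given here. Figure 3 is not shown and Form 1 is not reproduced. Either may carry the right schedule or settings, but the printed text would still conflict with itself.

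A reader might go further and infer that period 2 was in fact cut short, that treatment-first patients received no sham, or that the trial lost power. The documents support none of these. They do not record which instruction was followed, and they do not state the allocation ratio, so even the number of patients at risk cannot be given.

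**Conclusion.** The contradiction is established on the printed text. For period 2, Section 4C states 28 days, while its labels give about 12 to 15 days to the primary measurement and about 21 to 23 days to the laboratory visit. Period 1 gives about 26 to 29 and 28 to 30. The ranges assume programming on Day 0, 1 or 2 of the stated week; the 14-day shortfall on the primary measurement needs only that the same convention be used in both periods. The two programming instructions agree for sham-first patients and are incompatible for treatment-first patients.

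The labels are probably misnumbered, and the restore sentence is probably displaced from wrap-up. This is a moderate correction to operative text. The case for it is that the instructions conflict on treatment setting and on the timing of the primary endpoint. It does not rest on demonstrated harm, and any effect on power would depend on literal compliance and cannot be quantified from the documents.

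**What to change.** In Section 4C:

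1. Relabel the period 2 blood pressure test to Week 11 Day 0-1 and the laboratory visit and wrap-up to Week 11 Day 2.
2. Schedule both from the actual crossover programming date, so that each patient's exposure matches his or her own period 1. This matters because a full 7-day washout from Week 6 Day 2 (day 37 + 7 = 44) ends on Week 7 Day 2, while one week from Study Day 1 (day 1 + 7 = 8) ends on Week 2 Day 1. Fixed Week 11 labels could therefore differ from period 1 by a day.
3. Delete the restore-amplitude sentence from the crossover visit. Keep it at wrap-up, item 6.
4. Report, by period, the actual days from programming to the blood pressure test and the programmed voltage. Because the scheduling window remains, this lets readers see the exposure and setting each patient received.

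The cost is a wording amendment and two reported variables that can be taken from visit dates and device settings. No visit or procedure is added; the tests move to the week that the 28-day rule already implies.
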